#### **CONFIDENTIAL**

Takeda

REPLAGAL

ADA=anti-drug antibody; AE=adverse event; β-hCG=beta-human chorionic gonadotropin; BPI=Brief Pain Inventory; ECG=electrocardiogram; eGFR=estimated glomerular filtration rate; EOT=end of treatment; EOW=every other week; HCV=hepatitis C virus; IRR=infusion-related reaction; lyso-Gb3=globotriaosylsphingosine; PK=pharmacokinetic; SAE=serious adverse event

- a Screening procedures can be performed over multiple days within a period of up to 42 days following the subject's (or the subject's parent(s)/legally authorized representative) signature of the informed consent form.
- bAll baseline procedures and evaluations must be completed prior to the first REPLAGAL infusion and will be performed at the clinical site. Serum chemistry, hematology, urinalysis, and ECG performed at screening within 7 days prior to baseline visit may be used as the baseline.
- c During the treatment period, all study assessments and procedures should be completed on the day(s) of the scheduled visit.
- dThe REPLAGAL infusions are to be administered at the clinical site.
- eProcedures and evaluations to be performed at site visits will occur at the clinical site.
- f The safety follow-up period (end of study) is 14 days (+7 days) following EOT infusion (or the last infusion for discontinued subjects). During this period, there will be a telephone call/scheduled visit to query for AEs, SAEs, and concomitant medications. Subjects who experienced SAEs, or mild, moderate, or severe AEs may be requested to visit the clinical site for further examination. All AEs and SAEs that are not resolved at the time of this contact will be followed to closure.
- gFor subjects who discontinue the study early, all EOT assessments and procedures should be completed except for dose calculation and REPLAGAL infusion.
- hInformed consent must be obtained prior to performing any study-related procedures.
- i Fabry disease diagnosis will be confirmed at screening by medical record.

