- j The following vital signs will be collected at all study visits (screening and infusion visits): pulse, blood pressure, respiratory rate, and temperature. On infusion visits (EOW and evaluation visits), vital signs should be obtained as follows: 1) within 10 minutes prior to starting the infusion; 2) 20 minutes (±5 minutes) after the start of the infusion; 3) 10 minutes (±5 minutes) after completing the infusion; and 4) 30 minutes (±5 minutes) after completing the infusion. In the event that a scheduled infusion does not occur on an evaluation visit, the vital signs should still be collected. The vital signs that were taken within 10 minutes prior to the start of the expected infusion should be documented in the electronic case report form. If no IRRs are observed during the first 3 infusions, the observation and vital signs after infusion can be omitted at the discretion of the investigator.
- kFor subjects <18 years of age, height should be measured at screening, baseline, and every evaluation visit during the treatment period. For subjects  $\geq$ 18 years of age at screening, height should be measured only at the baseline visit.
- Weight will be measured at screening, baseline, and every visit during the treatment period, with any dosing adjustments completed prior to the dose administration.
- mAudiology testing is only applicable to subjects <18 years old.
- nThe first dose of REPLAGAL will be based on the subject's weight at baseline. A change of at least 5% in subject weight from baseline or the last weight used to calculate the dose will require a dose recalculation at the clinical site.
- oREPLAGAL (at a dose of 0.2 mg/kg body weight) will be administered as an intravenous infusion over 40 minutes (±10 minutes) EOW (±4 days) at the clinical site, except on Day 1 (Week 0) and at the Week 28 visit where the length of infusion must be exactly 40 minutes to support the PK sampling. All study procedures, assessments (except for post-infusion vital signs), and sample collections (except for post-infusion PK sample collection) should be completed prior to administering an infusion, except on Week 40 and 52 visits where REPLAGAL infusion should maintain the ±4 days window period while the evaluation procedures can be done within the ±7 days window period. If at all possible, missed infusions should be avoided. If a subject is not dosed within

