# 6.2.4 Dosing

REPLAGAL will be administered at a dose of 0.2 mg/kg body weight as an IV infusion over 40 minutes ( $\pm 10$  minutes) EOW ( $\pm 4$  days), except on Day 1 (Week 0) and Week 28 visits where the length of infusion must be exactly 40 minutes to support the PK sampling. The first dose of REPLAGAL will be based on the subject's weight at baseline.

The appropriate dose calculation is obtained as follows: multiply the subject's weight in kilograms by 0.2 mg/kg. (Round up or down to the 1/10th decimal place from the 1/100th decimal place using >0.05 to round up). This will give the number of milliliters of drug required since the concentration is 1 mg/mL. A change in subject weight of  $\geq$ 5% from baseline or the last weight used to recalculate the dose will require a recalculation of the dose by the clinical site.

REPLAGAL will be provided in single-use, 5 mL vials containing 3.5 mL of concentrate at a concentration of 1 mg/mL. To determine the number of vials required, divide number of milliliters determined above by 3.5 mL. Round up to the whole number and this is the number of vials required to withdraw the number of milliliters needed.

DOSE CALCULATION EXAMPLE for a subject weighing 68 kg:

 68 kg × 0.2 mg/kg = 13.6 mg of REPLAGAL (subject weight × 0.2 mg/kg required per protocol = subject total dose of REPLAGAL)

Since the concentration is 1 mg per mL, 13.6 mg = 13.6 mL

• 13.6 mL ÷ 3.5 mL = 3.9 vials (subject dose ÷ total volume per vial = number of vials required)

The subject would need 3 full vials and a partial amount of the fourth vial.

All study procedures, assessments (except for post-infusion vital signs), and sample collection (except for post-infusion PK sample collection) should be completed prior to administering an infusion, except on Week 40 and 52 visits where REPLAGAL infusion should maintain the  $\pm$ 4 days window period while the evaluation procedures can be done within the  $\pm$ 7 days window period.

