#### 6.2.5 Dose Modification

The first dose of REPLAGAL will be based on the subject's weight at baseline. A change of at least 5% in subject weight from baseline or the last weight used to recalculate the dose will require a dose recalculation at the clinical site. Weight will be measured at every infusion visit, as specified in the Schedule of Activities (Table 1), with any dosing adjustments completed prior to the dose administration.

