## 8.1.1 Screening Period (Week -7 to Week -2)

The duration of the screening period is up to 42 days where study subjects will undergo all procedures listed for the screening period in Table 1. The screening period can occur over multiple days to allow for the evaluation of subject's eligibility for inclusion in the study.

Written informed consent, and assent if applicable, to participate in the study will be obtained by the investigator from each subject before the performance of any protocol-specific procedure. The screening period starts when subjects sign informed consent/assent.

At screening, each subject will be reviewed for eligibility against the study inclusion/exclusion criteria. Subjects who do not meet the study entrance criteria will not be allowed to participate in the study, and the reason(s) for the subject's ineligibility will be documented.

A screen failure is a subject who has given informed consent but who fails to meet the inclusion and/or exclusion criteria and has not been administered investigational product(s).

Subjects who fail screening due to a single laboratory test result that does not meet eligibility criteria may have that laboratory test repeated at the discretion of the investigator. This will include a repeat of only the failed assessment rather than a repeat of all screening assessments (rescreening). In these cases, a new Subject Identification Code (SIC) is not required. The repeat of a single screening assessment is allowed only once. A repeat assessment must take place within 42 days of the initial screening for any subject requiring repeat of a screening assessment.

If this timeframe is exceeded, then all screening assessments must be repeated and the subject assigned a new SIC. Exemptions may be provided if the timeframe is exceeded due to administrative reasons.

Page 46

Subjects who still do not meet eligibility criteria may not have the laboratory test repeated a second time unless a justification can be provided.

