## 8.2.1.1 Height and Weight

Height and weight will be measured and recorded in the subject's source documents.

For subjects <18 years of age at screening, height should be measured at screening, baseline, and every evaluation visit during the treatment period.

For subjects  $\geq 18$  years of age at screening, height should be measured only at the baseline visit.

Weight is a critical measurement as it determines the dosing of REPLAGAL. Weight will be measured at screening, baseline, and every visit during the treatment period, as specified in the Schedule of Activities (Table 1), with any dosing adjustments completed prior to the dose administration (Section 6.2.5).

BMI should be calculated by the investigator using the weight and height measured during the baseline visit and will be recorded in the source documents as well as in EDC.

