6.0 STATISTICAL ANALYSIS

6.1 General Considerations

All statistical analyses will be performed using SAS[®] (SAS Institute, Cary, NC 27513) version 9.4 or higher.

Baseline values are defined as the last observed value before the first dose of study medication.

Means and medians will be presented to 1 more decimal place than the recorded data. The standard deviations (SDs) will be presented to 2 more decimal places than the recorded data. CIs intervals will be presented using the same number of decimal places as the parameter estimate.

Continuous variables will be summarized with descriptive statistics including the mean, standard deviation (SD), median, minimum and maximum. Categorical data will be summarized with the frequency and percentage of subjects falling within each category. Subsequently, longitudinal data will be analyzed using mixed-effects model for repeated measures (MMRM), using both the mITT and PP sets (using the PP set will serve as a sensitivity analysis).

The observed values, the change from baseline, the change over time, and the percentage change from baseline for the efficacy measurements (eGFR, urine protein/creatinine ratio, and plasma lyso-Gb3) will be summarized by sex and visit.

Subject listings will be provided for clinical outcomes from the BPI-Short Form measurement.

Audiology results will be produced at baseline and (if applicable) for each post-baseline evaluation visit.

Audiology data will also be presented in the form of individual subject listings.

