6.6.4 Extent of Exposure and Compliance

Treatment compliance and exposure summaries will be presented. For each subject, the subject's percent of compliance, reflecting the subject's willingness to accept the intravenous infusion at each infusion visit, will be calculated as follows for up to 52 weeks:

Compliance =

[(Number of Complete Infusions Received) / (Expected Number of Infusions)] ×100

Note: Expected number of infusions is defined as the number of infusions that the subject would have received up to the date of the subject's withdrawal or completion from the study. A non-complete / partial infusion is defined when the infusion has been withdrawn / stopped and not completed.

The number and percentage of subjects who received $\geq 80\%$ of scheduled infusions (not including partial infusions) will be reported. In addition, the total number of missed infusions will be categorized as 0, 1, 2 to 5, and >5 and summarized by n and the percentage in each category. The number of subjects with missed infusions will also be summarized.

The duration (in months) of drug exposure to REPLAGAL will be calculated as follows:

Exposure (months) = [(Date of the last dose – Date of first dose) + 1]/30.4375

The exposure data and the total number of infusions received will be summarized by descriptive statistics. The actual dose and per protocol dose amount (mg/kg) are defined as the weight adjusted **CONFIDENTIAL**

TAK675-3001	Page 23 of 27
Statistical Analysis Plan Amendment 1	1-Feb-2024

actual dose. For actual dose amount, the dose of REPLAGAL will be based on the last available weight on or prior to each infusion date. For protocol dose amount, the first dose of REPLAGAL will be based on the subject's weight at screening. The actual and per protocol dose amounts (mg/kg) and durations of infusion (minutes) will be averaged across the non-missing infusions for each subject and then summarized by the descriptive statistics across all subjects. All exposure data will be presented in a by-subject listing.

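### SAP 6.6.4 takes the first-infusion per-protocol dose from screening weight, whereas the protocol doses on baseline weight; one descriptive exposure row and its listing are affected

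*SAP*

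**What the plan says.** SAP 6.6.4 reports two weight-adjusted dose amounts in mg/kg. The actual amount uses the most recent weight recorded up to and including each infusion date. For the per-protocol amount, the "first dose of REPLAGAL will be based on the subject's weight at screening". Both are averaged over each subject's non-missing infusions, summarised descriptively across subjects, and listed by subject. The SAP gives no reference weight for the per-protocol amount after the first infusion.

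The protocol's rule is: "The first dose of REPLAGAL will be based on the subject's weight at baseline". It appears in Table 1 footnote n and again in Sections 6.2.4, 6.2.5 and 8.1.3.1. Recalculation is triggered by "A change of at least 5% in subject weight from baseline or the last weight used to recalculate the dose" (Section 6.2.5).

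On timing, "Weight will be measured at screening, baseline, and every visit during the treatment period" (protocol 8.2.1.1). Screening runs from Week -7 to Week -2 and "The duration of the screening period is up to 42 days" (protocol 8.1.1); the baseline visit is at Week -1.

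**The concern.** The per-protocol row is useful only if it sets the dose given against the weight the protocol prescribes for dosing. With screening weight as the reference, a subject dosed correctly on baseline weight departs from 0.200 mg/kg, while a subject dosed wrongly on screening weight shows exactly 0.200. For the first infusion the row therefore points the wrong way.

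The silence about later infusions adds to this. Two programmers could produce different tables from the same sentence: one confining screening weight to infusion 1, the other carrying it forward until a 5% change.

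The stakes are limited to one descriptive row and its listing. Dose given, compliance, exposure duration, efficacy and the serious TEAE endpoint do not use this weight, and SAP 3.1 plans no hypothesis test.

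**Working it through.** **Is the difference real?**

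- The protocol gives baseline weight in all four places that state the first-dose rule. None uses screening weight.
- Screening values may stand in for baseline only for listed items: "Serum chemistry, hematology, urinalysis, and ECG performed at screening within 7 days prior to baseline visit may be used as the baseline" (Table 1 footnote b). Footnote q does the same for an earlier echocardiogram. Weight is in neither.
- SAP 8.0 lists no change to the protocol-planned analyses. The SAP 9.1 change log entry for 6.6.4 concerns only the weight used for the actual dose amount.

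So the SAP states a different rule and does not declare it as a choice.

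**Size of the effect**

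Inputs from the documents: dose 0.2 mg/kg; infusions every other week from Week 0 to Week 52, so 52/2 + 1 = 27; recalculation at a weight change of 5% or more; doses rounded to 0.1 mL at 1 mg/mL. The protocol's own example reproduces: 68 × 0.2 = 13.6 mg, and 13.6/68 = 0.200 mg/kg.

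Assumptions: a full course of 27 infusions; no weight change after baseline; per-protocol amount = dose given / reference weight; a screening-to-baseline change *c*, for which the documents give no figure. Dose rounding is ignored in the table.

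First-infusion value = 0.2 × (baseline weight / screening weight) = 0.2 × (1 + *c*).

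Subject mean, infusion 1 only = [0.2 × (1 + *c*) + 26 × 0.2] / 27, a relative shift of *c*/27.

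| *c* | First-infusion value | Subject mean, infusion 1 only | Shift |
|---|---|---|---|
| ±1% | 0.198 / 0.202 | 0.19993 / 0.20007 | 0.04% |
| ±2% | 0.196 / 0.204 | 0.19985 / 0.20015 | 0.07% |
| ±4.9% | 0.1902 / 0.2098 | 0.19964 / 0.20036 | 0.18% |

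If screening weight is carried forward and replaced only at a 5% change, a 4.9% difference persists through all 27 infusions and the subject mean is itself 0.1902 or 0.2098. At 5% or more the rule replaces the weight at the next infusion. At +6%, infusion 1 is 0.212 and the mean is (0.212 + 26 × 0.2)/27 = 0.2004.

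**Comparison with permitted rounding**

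The protocol rounds the dose: "Round up or down to the 1/10th decimal place from the 1/100th decimal place" (Section 6.2.4). The largest effect is 0.05 / (0.2 × weight): 0.05/6 = 0.83% at 30 kg and 0.05/12 = 0.42% at 60 kg. Both exceed the largest infusion-1-only shift shown.

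**An invented subject**

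Screening weight is 30.0 kg; weight at baseline and Day 1 is 31.4 kg.

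- Correct dose: 31.4 × 0.2 = 6.28, rounded to 6.3 mg. Per-protocol row: 6.3/30.0 = 0.210. Actual-dose row: 6.3/31.4 = 0.201.
- Wrong dose, based on screening weight: 6.0 mg. Per-protocol row: 6.0/30.0 = 0.200. Actual-dose row: 6.0/31.4 = 0.191.

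The per-protocol row flags the correct dose and passes the wrong one. The actual-dose row shows the error.

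**The case against.** The strongest reply is that nothing visible changes. The disputed sentence covers only the first dose, and averaging over 27 infusions dilutes it to less than permitted rounding can produce. If means were shown to three decimals, 0.20036 and 0.19964 would both print as 0.200. The actual-dose row already exposes most misdosing. This stands, and it is why the point is minor. It does not cover the by-subject listing, where the first-infusion value appears undiluted.

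A second objection is that the protocol's 5% rule compares with baseline weight or the last weight used, never with screening weight. Applied literally from infusion 2, it brings baseline weight back and leaves only the first-infusion effect. That is a fair reading. The carry-forward and 6% figures are therefore conditional on the SAP's silence and are not its stated method.

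Third, the SAP gives no formula, so dose given over reference weight is an interpretation. It follows from the SAP's description of both amounts as weight-adjusted actual dose, but it remains a reading.

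Finally, naming the Week -1 visit raises two edge cases. A missing baseline weight is already covered by the screening fallback in SAP 9.2.2. A change of 5% or more between Week -1 and Day 1 could trigger recalculation of the first dose itself; that is a remote case and does not make the fix unsound.

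**Conclusion.** The concern holds, as a minor point. The SAP states a reference weight that contradicts the protocol, and the first-infusion per-protocol value is wrong as written for any subject whose weight changes between screening and baseline. Confidence in the text mismatch is high.

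The size rests on assumed weight changes and on the reading of the amount as dose given over reference weight. It is negligible for the subject mean if only infusion 1 is affected, and reaches just under 5% only on the carry-forward reading.

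**What to change.** In SAP 6.6.4, replace screening weight with the weight at the baseline visit (Week -1), described as the weight the protocol prescribes for the first dose. Writing only *baseline* would leave an ambiguity. SAP 6.1 says "Baseline values are defined as the last observed value before the first dose of study medication", and weight is also measured at the Week 0 infusion visit, so the word could be read as the Day 1 weight.

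Add that later infusions use the last weight used for dose calculation under the 5% rule in protocol 6.2.5. A cross-reference to SAP 9.2.2 would make the fallback for a missing Week -1 weight explicit.

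The cost is SAP wording and the programming of one derived variable. All the weights are already collected.

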6.7 Pharmacokinetic, Pharmacodynamic, and Biomarker Analyses

6.7.1 Pharmacokinetic Analysis

Serum PK concentrations and PK parameters will be presented according to CPAP.

6.7.2 Pharmacodynamic Analysis

The observed values, the change from baseline, the change over time, and the percentage change from baseline for the plasma lyso-Gb3 will be summarized by sex and visit.

6.7.3 Biomarker Analysis

Not applicable.

6.8 Patient Reported Outcomes (PROs) and Health Care Utilization Endpoints Analysis

6.8.1 PRO Analysis

Subject listings will be provided for clinical outcomes from the BPI-Short Form measurement.

6.8.2 Health Care Utilization Analysis

Not applicable.

6.9 Other Analyses

Not applicable.

6.10 Interim Analyses

No interim analysis will be performed.

6.11 Data Monitoring Committee/Internal Review Committee/ [Other Data Review Committees]

Not applicable.

7.0 **REFERENCES**

Not applicable.

8.0 CHANGES TO PROTOCOL PLANNED ANALYSES

Not applicable.

9.2 Data Handling Conventions

9.2.1 General Data Reporting Conventions

Means and medians will be presented to 1 more decimal place than the recorded data. The standard deviations (SDs) will be presented to 2 more decimal places than the recorded data. CIs will be presented using the same number of decimal places as the parameter estimate. When the original data have 3 or more decimal places, the same rule as for 3 decimal places would apply to all.

For categorical variables, the count (n) and percent (%) will be displayed. Unless otherwise stated in table shells, the denominator for percentages is N (the number of subjects in the treatment group within that analysis set). For any summary by subgroups (e.g. by sex), the denominator is the number of subjects in that subgroup/treatment group within that analysis set.

- Percentages will be reported to 1 decimal place, except when the percentage equals exactly 100 where it will be displayed as an integer (100). For zero, only count and no percentage will be displayed.
- For summaries of categorical variables percentages are usually based on N as stated above. However, if missing is not a category then the denominator is the number of subjects with non-missing values. Any exceptions to the denominator should be explained in the footnotes.

9.2.2 Definition of Baseline

Baseline will be defined as the data collected prior to the first administration of study drug. If the value prior to first administration is not available, the screening value will be used.

TAK675-3001	Page 26 of 27
Statistical Analysis Plan Amendment 1	1-Feb-2024

9.2.3 Definition of Visit Windows

For the efficacy analysis, compare the unscheduled visit date to the closest infusion date greater or equal than the unscheduled visit date; if the unscheduled visit occurred on or within 4 days of that infusion date then we assign the infusion week as the visit week for the unscheduled visit. The assessment result from the unscheduled visit will be used to replace the missing result for that visit week.

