## 4. STUDY DESIGN

## 4.1 Overall Design

This is a China-only, Phase 3, multicenter, nonrandomized, open-label, single-arm study to evaluate the safety, efficacy, and PK of REPLAGAL in treatment-naïve Chinese subjects with Fabry disease. The study will consist of EOW treatment with 0.2 mg/kg IV infusion of REPLAGAL for up to 52 weeks. A total of 20 safety evaluable subjects aged  $\geq$ 7 to  $\leq$ 65 years are planned to be enrolled with at least 25% of the total eligible subjects in the age range of  $\geq$ 7 to <18 years old.

The study will include a screening period, a baseline visit period, a treatment period, and a safety follow-up period. Screening assessments will occur from Week -7 through Week -2. Baseline visit period will be at Week -1. After completion of baseline procedures and assessments, eligible subjects will receive 0.2 mg/kg IV infusions of REPLAGAL EOW (±4 days) from Day 1 (Week 0) up to Week 52 (end of treatment [EOT] visit) during the treatment period. Evaluation visits will be performed at clinical site at Week 8 (±4 days), Week 16 (±4 days), Week 28 (±4 days), Week 40 (±7 days), and Week 52 (±7 days). Additionally, PK assessments will occur at Day 1 (Week 0) and Week 28 (±4 days). In order to ensure subjects' safety, subjects will undergo a follow-up period of approximately 14 days (+7 days) after the completion of the treatment infusion (or the last infusion for early treatment discontinued subjects). The complete list of study procedures is presented in Table 1.

In the event a monitor cannot visit the site in a timely manner due to unavoidable circumstances, such as the coronavirus disease (COVID-19) pandemic, alternative monitoring approaches such as remote source data verification or telephone contact may be used to ensure data quality and integrity and maintain subject safety. Alternative monitoring approaches should be used only where allowed by the local Health Authority and permitted by the institutional review board (IRB)/ethics committee (EC), if applicable.

Safety assessments include monitoring of AEs, use of concomitant medication, clinical laboratory values, vital signs, antibody formation, physical examination, and electrocardiogram (ECG) results (Section 8.2.3).

Efficacy assessments include measurements of eGFR, urine protein/creatinine ratio, LVMI, LVEF, and Brief Pain Inventory (BPI). For pediatric subjects (<18 years old at screening), additional assessment for hearing will be performed (Section 8.2.2).

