## 8.1.3 Treatment Period

# 8.1.3.1 REPLAGAL Infusion EOW (±4 days) from Week 0 Through Week 52

The treatment period will be up to 52 weeks during which subjects will receive EOW ( $\pm$ 4 days) IV infusions of REPLAGAL at the clinical site. The first dose of REPLAGAL will be based on the subject's weight at baseline. A change in subject weight of  $\geq$ 5% from baseline or the last weight used to recalculate the dose will require a recalculation of the dose by the clinical site.

# 8.1.3.2 Evaluation Visits at Week 8, 16, 28, 40, and 52

At evaluation visits, all study procedures, assessments (except for post-infusion vital signs), and sample collection (except for post-infusion PK sample collection on Week 28) outlined in Table 1 should be completed prior to administering an infusion, except on Week 40 and 52 visits where REPLAGAL infusion should maintain the  $\pm$ 4 days window period while the evaluation procedures can be done within the  $\pm$ 7 days window period. If REPLAGAL is discontinued, regardless of the reason, the evaluations listed for Week 52 will be performed as completely as possible. Subject may visit the clinical site at schedules other than the scheduled visits for assessments as clinically warranted; these will be recorded as unscheduled visit. Unscheduled visit(s) will be recorded in the eCRF.

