2.0 STUDY DESIGN

This is a China-only, Phase 3, multicenter, nonrandomized, open-label, single-arm study to evaluate the safety, efficacy, and PK of REPLAGAL in treatment-naïve Chinese subjects with Fabry disease. The study will consist of EOW treatment with 0.2 mg/kg IV infusion of REPLAGAL for up to 52 weeks. A total of 20 safety evaluable subjects aged \geq 7 to \leq 65 years are planned to be enrolled with at least 25% of the total eligible subjects in the age range of \geq 7 to <18 years old.

The study will include a screening period, a baseline visit period, a treatment period, and a safety follow-up period. Screening assessments will occur from Week -7 through Week -2. Baseline visit period will be at Week -1. After completion of baseline procedures and assessments, eligible subjects will receive 0.2 mg/kg IV infusions of REPLAGAL EOW (±4 days) from Day 1 (Week 0) up to Week 52 (end of treatment [EOT] visit) during the treatment period.

Evaluation visits will be performed at clinical site at Week 8 (± 4 days), Week 16 (± 4 days), Week 28 (± 4 days), Week 40 (± 7 days), and Week 52 (± 7 days). Additionally, PK assessments will occur at Day 1 (Week 0) and Week 28 (± 4 days). In order to ensure subjects' safety, subjects will undergo a follow-up period of approximately 14 days (± 7 days) after the completion of the treatment infusion (or the last infusion for early treatment discontinued subjects).

In the event a monitor cannot visit the site in a timely manner due to the coronavirus disease (COVID-19) pandemic, alternative monitoring approaches such as remote source data verification or telephone contact may be used to ensure data quality and integrity and maintain subject safety. Alternative monitoring approaches should be used only where allowed by the local Health Authority and permitted by the institutional review board (IRB)/ethics committee (EC), if applicable.

Safety assessments include monitoring of AEs, use of concomitant medication, clinical laboratory values, vital signs, antibody formation, physical examination, and ECG.

Efficacy assessments include measurements of eGFR, urine protein/creatine ratio, and Brief Pain Inventory (BPI). For pediatric subjects (<18 years old at screening), additional assessment for hearing will be performed.

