9.2.4 Handling of missing data

Imputation of missing data post-baseline will be employed using last observation carried forward (LOCF) for the endpoints of the change from baseline to subsequent time points in eGFR, LVMI, LVEF, lyso-Gb3 and urine protein / creatinine ratio. No data imputation will be done for the categorical analyses of the BPI (short form).

Imputation of missing dates 9.2.5

Any date that is collected only as MONTH / YEAR, e.g., date of birth, the 15th of the month will be imputed.

If AE start date is partial, the following imputation will be done:

- If day is missing, impute 1st of the month
- If day and month are missing, impute 01 July. However, this should be checked not to be later than the AE stop date. If AE stop date is available, the 1st of the month of the AE stop month should be imputed,

If AE stop date is partial, the following imputation will be done:

- If day is missing, impute end of the month $(30^{\text{th}} \text{ or } 31^{\text{st}})$
- If day and month are missing, impute 31 Dec.

If AE stop date is missing (i.e., AE still ongoing), and AE start date has missing day and month, and imputed AE start date per above rules (01July) is after date of death (DTHDT) or end of study date (EOSDT) then "01Jan" will be imputed as AE start date.

If imputed stop date is after date of death (DTHDT) or end of study date (EOSDT), AE end date will be imputed as date of death (DTHDT) or end of study (EOSDT).

The same rules above (for AE date imputation) will be followed for prior / concomitant medications and medical history.

TAK675-3001	Page 27 of 27
Statistical Analysis Plan Amendment 1	1-Feb-2024

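### The SAP's unscheduled-visit rule reaches only part of the ±7-day Week 40 and Week 52 windows, so LOCF can be used although an in-window value was observed

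*SAP*

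**What the plan says.** SAP 9.2.3 is the SAP's only text on visit windows, and it deals only with unscheduled visits in the efficacy analysis. The programmer is to "compare the unscheduled visit date to the closest infusion date greater or equal than the unscheduled visit date", and the infusion's week is assigned "if the unscheduled visit occurred on or within 4 days of that infusion date". The purpose is stated next: "The assessment result from the unscheduled visit will be used to replace the missing result for that visit week". The rule looks forward only, is 4 days wide, and is the same for every visit week.

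Protocol 4.1 gives the late evaluation visits a wider window, "Week 40 (±7 days), and Week 52 (±7 days", and SAP 2.0 repeats it. Footnote o of Protocol Table 1 separates the two activities at these visits: the infusion keeps its ±4 days "while the evaluation procedures can be done within the ±7 days window period". Protocol 6.2.4 and 8.1.3.2 say the same. A Week 40 or 52 evaluation may therefore properly follow the infusion.

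For values still missing, SAP 9.2.4 states: "Imputation of missing data post-baseline will be employed using last observation carried forward (LOCF", covering change from baseline in eGFR, LVMI, LVEF, lyso-Gb3 and urine protein/creatinine ratio. SAP 6.5.2 restricts Week 52 analyses to subjects who complete 52 weeks of treatment.

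**The concern.** The rule for rescuing a missing visit is tied to the next infusion, whereas the protocol defines the Week 40 and 52 evaluations by a window around the target day. The two do not match. Take a subject whose scheduled Week 52 result is missing but who has an unscheduled measurement a few days after the Week 52 infusion. That measurement is inside the protocol's window, yet it has no later infusion to attach to. The week stays missing and LOCF supplies an older value.

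Week 52 change in eGFR is a named secondary endpoint, and Week 52 is the last on-treatment assessment of every efficacy measure. The cost is greatest for echocardiography, which Protocol Table 1 schedules only at baseline, Week 16 and Week 52.

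**Working it through.** The documents give no figure for this point, so there is none to reproduce. The check applies the SAP 9.2.3 rule to each calendar day of the protocol window.

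**Inputs**
- Window at Weeks 40 and 52: days -7 to +7 around the target day, 7 + 1 + 7 = 15 days (Protocol 4.1, SAP 2.0).
- Infusions every 14 days, each allowed ±4 days (Protocol 6.2.4).
- A day v is assigned to the visit if the first infusion on or after v is that visit's infusion, on day d, and d - v ≤ 4 (SAP 9.2.3).
- Assumption: only the visit's own infusion is moved, to day -4, 0 or +4.

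**Result for Weeks 40 and 52**

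| Infusion day | Days assigned to the visit | Count | Not assigned |
|---|---|---|---|
| 0 (target) | -4 to 0 | 5 of 15 | 10 |
| -4 | -7 to -4 | 4 of 15 | 11 |
| +4 | 0 to +4 | 5 of 15 | 10 |

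With the infusion on target, days -7 to -5 (3 days) and +1 to +7 (7 days) are out of reach: 3 + 7 = 10. If a subject has no Week 52 infusion, 0 of 15 days can be assigned to Week 52. The SAP does not say whether such a subject counts as a 52-week completer.

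**After the last infusion.** No later infusion date exists, so nothing dated after it can be assigned. Results 0 to 4 days before a Week 52 infusion do map to Week 52.

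**Assignment to another week.** If the Week 42 infusion is given 4 days early, it falls on day 14 - 4 = +10 from the Week 40 target. Unscheduled results on days +6 and +7 are then within 4 days of it and are labelled Week 42, which has no evaluation visit, although they lie in the Week 40 window.

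**Age of the value carried forward**, if the preceding scheduled value was observed:
- LVMI and LVEF at Week 52: 52 - 16 = 36 weeks.
- eGFR, lyso-Gb3 and urine protein/creatinine ratio: 52 - 40 = 12 weeks at Week 52, and 40 - 28 = 12 weeks at Week 40.

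**Weight of one subject.** 1/20 = 5% of the planned sample. Protocol 6.5 assumes 10% to 20% drop-out, leaving 18 to 16 subjects, so one is 1/18 = 5.6% to 1/16 = 6.3% of a completer analysis. The share is larger in the by-sex summaries.

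**The case against.** The strongest reply is that this is a rescue rule for extra visits, not the analysis window. That is right. A reader might infer that the SAP drops valid Week 40 and 52 evaluations done within ±7 days; the documents do not support this. An evaluation at day -7 or +7 is still the scheduled visit, and no text removes it. Under Protocol 8.1.3.2 an unscheduled visit is something else: "Subject may visit the clinical site at schedules other than the scheduled visits for assessments as clinically warranted". A late Week 52 echocardiogram could often be recorded as the Week 52 evaluation itself. Harm needs a missing scheduled result, an in-window measurement recorded as unscheduled, and a date the rule does not reach.

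A reader might also infer that no unscheduled result can ever fill Week 52. That is too strong, because results up to 4 days before the Week 52 infusion do.

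The forward direction also has a basis. The protocol generally wants assessments finished before the infusion, with a timing exception only at Weeks 40 and 52. Protocol 8.2.4.1 asks for lyso-Gb3 before the infusion, and 8.2.2.2 asks the same for the BPI-Short Form, neither stating an exception. A symmetric window for every visit and measure would create a new conflict. This limits the remedy, but it does not explain a 4-day forward rule for eGFR, urine protein/creatinine ratio or echocardiography at Weeks 40 and 52.

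Finally, the day counts are not counts of results. The SAP tests no hypothesis, so no error rate is at stake.

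**Conclusion.** The mismatch is real and narrow. At Weeks 40 and 52 the rule reaches 4 or 5 of 15 in-window days at the infusion timings tested. An unscheduled value on the other days cannot fill a missing result, so a value 12 weeks older, or 36 weeks older for LVMI and LVEF at Week 52, is carried forward instead.

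The conclusion rests on two readings. First, an unassigned unscheduled value is taken to be unused for that visit; the SAP does not say so, but gives no other route for it. Second, LOCF is taken to apply to the change-from-baseline summaries; the SAP does not say whether carried-forward values also enter the MMRM. The number of subjects affected cannot be derived from the documents and is probably small. With about 16 to 18 completers, even one is visible in a Week 52 mean. This is a worthwhile clarification, not a threat to the study's conclusions.

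**What to change.** Amend SAP 9.2.3 for Weeks 40 and 52: when the scheduled result is missing, assign an unscheduled efficacy result to the visit if it falls within ±7 days of the target day. Use the value closest to the target day, with ties going to the pre-infusion value. Apply this before any LOCF under SAP 9.2.4, and let it take precedence over assignment to a non-evaluation week.

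Keep the pre-infusion condition for lyso-Gb3 and the BPI-Short Form at Weeks 40 and 52, so that only results taken before that visit's infusion qualify. Leave the present rule unchanged at Weeks 8, 16 and 28. One added sentence should confirm that scheduled evaluations are analysed under their nominal visit.

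The cost is a short SAP edit and a small programming change, with no new data. The downside is that some Week 40 and 52 values will be post-infusion, which the protocol already allows at those visits.
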